## 5.1 Study Design

This will be an ***observational***, longitudinal case-crossover study nested within a cohort study, following up to 730 Veterans seen for LBP in VA primary care prospectively for 12 months. Study procedures will not make changes to nor in any way affect the typical medical care for LBP provided at VAPSHCS. **All study assessments following recruitment will be “e-Questionnaires” that participants complete using their own personal electronic devices (smartphones, tablets, or PCs, not provided by the study).** There are two types of e-Questionnaires that participants will complete: “*scheduled e-Questionnaires*” and “*flare window e-Questionnaires*”. Scheduled e-Questionnaires are quasi-random, ‘cue-elicited’ frequent assessments that will be repeated numerous times throughout the 1-year follow-up period. Cues to complete scheduled e-Questionnaires are automated “e-Alert” notifications sent by text message and email at the start of each “*scheduled assessment window*”, the 3-hour period during which a scheduled e-Questionnaire may be completed. ***Scheduled e-Questionnaires will occur three times each week during weeks 1-4 of follow-up, once a week during weeks 5-8, and twice a month during months 2-12.*** Participants will also complete unscheduled “*flare window e-Questionnaires*” on an *ad hoc* basis, if they experience new flares of LBP at any time during the 1-year follow-up period. At study entry, participants will receive training on how to complete flare window e-Questionnaires, if they experience flares of pain, by logging on to a secure Participant Portal (the **Flares of LBP with Activity Research Study** or “FLARES” website) within 3 hours after the onset of a new pain flare. In addition, all scheduled e-Questionnaires will remind participants to complete a flare window e-Questionnaire if they have a new pain flare. Scheduled e-Questionnaires and flare window e-Questionnaires generally contain the same question items, however, scheduled e-Questionnaires inquire about activity exposures *preceding the start of the scheduled assessment window* (when e-Alert notifications are sent), and flare window e-Questionnaires inquire about activity exposures *over the time period preceding the flare onset*. Each e-Questionnaire will begin by prompting the participant with the definition of a LBP flare. Participants will then report whether or not they are experiencing a flare, the primary outcome for Aim 1 of this study. E-Questionnaires will also inquire about activity exposures that have occurred over the 24-hour period prior to the assessment window start and - *if* an activity is reported – ask for further clarification of whether the activity was performed in the 2-hour period prior to the assessment window start. Further questions included in every e-Questionnaire are time-varying pain and psychological covariates (pain intensity, depression, catastrophizing, stress, etc.) assessed using brief, validated measures. All e-Questionnaires are inherently time lagged for activity-flare relationships, since they capture *current* flare status at time=t, and activities in the 24-hour period *before* the start of the assessment window/flare onset (t-1). Participants may also be offered to wear the optional ActiGraph wGT3X-BT unit continuously for weeks 1-4 of the study. Due to the participant burden involved with frequent serial e-Questionnaire assessments, a run-in period during weeks 1 and 2 of follow-up will exclude those individuals unable to maintain compliance with these assessments. Aim 1 analyses will examine the short-term effects of 10 specific activity categories on participant-reported flares across all study assessments over 1-year follow-up. Aim 2 analyses will examine associations between the frequency of exposure to 10 specific activity categories over weeks 1-4 of follow-up, and long-term functional recovery at 12 months as defined by the RMDQ. All analyses will use a biopsychosocial framework accounting for potential confounders (sociodemographics, psychological factors, etc.) and effect modifiers, and will include sensitivity analyses to examine the robustness of findings and important study assumptions.

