#### 5.2.5 Run-in period

Participants who join the study may subsequently fail requirements of the 2-week run-in period and be withdrawn from the study. A run-in period is needed for a study of this type to ensure that participants are able to complete the frequency of data collection that is necessary for the study to be valid. Criteria for failing the run-in period include (1) not completing the baseline e-Questionnaire, (2) not completing at least 4 of 6 e-Questionnaires in the 2-week run-in period, with an adequate proportion of e-Questionnaire items completed within surveys, as the definition for completion, or (3) not completing the UW informed consent for the (non-VA) UW component of the study; although listed separately to be explicit, completing the UW informed consent (3) is necessary before a participant is able to complete (1) and (2). These criteria could be waived or more time allotted if participants report a major life event (unexpected illness, injury, etc.) preventing a criterion from being met or are otherwise determined to be eligible by research staff on a case-by-case basis.

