**5.6.2b. Aim 2 analyses:** We will examine associations between the frequency of activity during scheduled e-Questionnaires (% of periods during which each of the 10 primary activity categories were reported over the 1st 4 weeks of follow-up), and the outcome of long-term LBP-related functional limitations at 12 months as reflected by the RMDQ, using a Bonferroni-corrected threshold of p=0.005 (**Figure 4**). Activity over the 1st 4 weeks is the exposure of interest for the Aim 2 analysis because activity restriction is most expected early in an episode of LBP, and because of our previously-stated reasoning that early changes in activity may be particularly important in determining long-term/overall activity-function relationships. The percentage of periods with each activity category over the 1st 4 weeks will be calculated from self-reported activity information and ActiGraph output. The main multivariate model for each activity category will explicitly adjust for a range of potential confounders based on prior knowledge and conceptual rationale, including baseline RMDQ score, and all psychological predictors and other baseline covariates. We will then conduct secondary analyses analogous to that done for Aim 1 to examine activity-1-year-RMDQ associations after accounting for important relationships based on theory and prior knowledge: potential moderation by baseline employment status, compensation status, or job satisfaction; potential moderation by analgesic use over the first 4 weeks of follow-up; sensitivity analyses contrasting associations with cumulative activity exposure early (weeks 1-2) vs. late (weeks 3-4 or weeks 5-8).

during follow-up; and clinical subgroup analyses (LSRS and SLSS subgroups). We will use the same approach for the secondary outcomes of LBP intensity, lost work productivity, quality of life, and analgesic use at 1-years.

Analyses for Aims 1 and 2 will use VA administrative data to weight the sample of participants back to represent the target population of Veterans with back pain (including those who did not respond to the study).

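### The self-reported Aim 2 exposure rests on at most 12 reports and is analysed as if free of sampling error, so the 1-year RMDQ slopes are biased toward zero by an unstated amount

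*Combined protocol and SAP*

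**What the plan says.** Section 5.6.2b regresses the 12-month RMDQ on the percentage "of periods during which each of the 10 primary activity categories were reported over the 1 st 4 weeks of follow-up", one model per activity category, at a threshold of p=0.005. The percentage "will be calculated from self-reported activity information and ActiGraph output".

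The number of reports follows from section 5.1: "Scheduled e-Questionnaires will occur three times each week during weeks 1-4 of follow-up, once a week during weeks 5-8". Each questionnaire asks about "activity exposures that have occurred over the 24-hour period prior to the assessment window start".

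Section 5.2.5 fails a participant for "not completing at least 4 of 6 e-Questionnaires in the 2-week run-in period", so 4 of 6 is enough in weeks 1-2. I found no stated minimum for weeks 3-4.

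Section 5.6.2b also plans "sensitivity analyses contrasting associations with cumulative activity exposure early (weeks 1-2) vs. late (weeks 3-4 or weeks 5-8", and explains the focus on weeks 1-4 by the expectation that early changes in activity may matter most.

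The plan gives no reliability estimate, measurement-error model or minimum report count for this exposure. The missing-data plan in section 5.6.2 is written around missing outcomes, not sampling error in an exposure.

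**The concern.** A percentage from 12 yes/no reports is a noisy measure of how often a person does an activity. At a frequency of 20%, binomial error alone has an SD of √(0.16/12) = 0.115, or 11.5 percentage points. A regressor with such error gives a slope that is too close to zero, and a larger n does not cure it.

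The slopes matter beyond the test. Section 5.6.3 will table them as long-term effects, set them beside the short-term ones, and use the combination to discuss whether an activity might be avoided or encouraged. One of its worked examples turns on an activity having no effect on 1-year function. Attenuation makes that reading more likely for an activity that does have an effect.

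The early-late contrast has a separate difficulty. Weeks 5-8 supply fewer reports than weeks 1-2, so the later slope is attenuated more. That difference runs in the direction the plan already expects.

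**Working it through.** **Inputs from the documents**
- Reports (5.1): 3 × 4 = 12 in weeks 1-4, so 6 in weeks 1-2 and 6 in weeks 3-4; 1 × 4 = 4 in weeks 5-8. At most 12 of 28 days (43%) are observed.
- Aim 2 power statement (5.6.1): n = 440, RMDQ SD 6.4, α = 0.005, activity frequency about 20%, 2.5 points per 65% change in frequency, power at least 80%.

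**Not given, so assumed:** a two-sided test; the 65% read as 0.65 on the proportion scale; covariates explaining between 0 and 50% of RMDQ variance (R²).

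**1. The plan's own figures.** 440/(1 − 0.40) = 733.3, rounded up to 734, against 730 stated. 290/730 = 39.7%, against 40%. 0.05/10 = 0.005. These agree. The 80% power can be neither reproduced nor refuted, because the between-person SD of frequency is not stated. I therefore solved for the SD that gives exactly 80%.

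**2. SD implied by 80% power.** Power = Φ(β·SDx·√n / SDres − 2.807), with β = 2.5/0.65 = 3.85. Setting power to 80%:
- R² = 0: SDx = (2.807 + 0.842) × 6.4 / (3.846 × 20.98) = 0.289
- R² = 0.5: SDx = 0.289 × √0.5 = 0.205

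**3. Implied ICC.** Let the ICC be the between-person variance of underlying frequency divided by m(1 − m) = 0.20 × 0.80 = 0.16.
- If SDx is the SD of true frequency, ICC = SDx²/0.16, which gives 0.52 (R² = 0) and 0.26 (R² = 0.5).
- If SDx is the SD of the observed 12-report percentage, SDx²/0.16 = ICC + (1 − ICC)/12, which gives 0.48 and 0.195.

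The range is about 0.20 to 0.52.

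**4. Attenuation.** With underlying frequency as the target, λ = k·ICC / (1 + (k − 1)·ICC). At k = 12 the four ICCs 0.195, 0.26, 0.48 and 0.52 give λ = 0.74, 0.81, 0.92 and 0.93, a dilution of 26%, 19%, 8% and 7%. If the target is the actual 28-day percentage, λ = [ICC + (1 − ICC)/28] / [ICC + (1 − ICC)/k].

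| ICC | λ, 12 reports | λ, 8 reports | λ, 12 reports, 28-day target |
|---|---|---|---|
| 0.064 | 0.45 | 0.35 | 0.69 |
| 0.10 | 0.57 | 0.47 | 0.76 |
| 0.20 | 0.75 | 0.67 | 0.86 |
| 0.25 | 0.80 | 0.73 | 0.89 |
| 0.40 | 0.89 | 0.84 | 0.94 |
| 0.50 | 0.92 | 0.89 | 0.96 |

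A simulation of the naive slope (400 replicates, n = 440, all 12 reports) gave λ = 0.46, 0.56, 0.79 and 0.90 at ICC 0.064, 0.10, 0.25 and 0.40. With an assumed 80-85% completion it gave 0.40, 0.50, 0.76 and 0.86.

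Adjustment can add to the dilution. If the covariates explain 20% of the observed exposure (an assumption), λ = 0.75 becomes (0.75 − 0.20)/(1 − 0.20) = 0.69.

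**5. Early versus late.** Ratio of λ with 4 reports to λ with 6:
- ICC 0.20: 0.500/0.600 = 0.83, so weeks 5-8 are 17% smaller
- ICC 0.52: 0.813/0.867 = 0.94, so weeks 5-8 are 6% smaller

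Weeks 1-2 and weeks 3-4 both have 6 reports, so the ratio by design is 1.

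**6. Dependence on the 65% reading.** A relative change would be 0.65 × 0.20 = 0.13, and the required SD 0.289 × 0.13/0.65 = 0.058. That is below the 0.115 of binomial error, so it could only be an SD of true frequency, with ICC 0.058²/0.16 = 0.02 and much heavier dilution. The 7-26% is tied to the proportion-scale reading.

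**The case against.** The best defence is that the documents do not show the dilution to be large. A reader might assume between-person SDs of 10 to 20 percentage points and infer a loss of roughly 20-55%. Those SDs are not in the plan and fit its power statement poorly. At the corresponding ICCs of 0.064 to 0.25, even a perfectly measured exposure would have only 6% to 39% power with no covariate R². That objection stands, and the range should be tied to the plan's own figures.

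A reader might also infer that estimates will miss a 2.5-point threshold. The documents do not support this: 2.5 points is a planning value tied to a 65% contrast in 5.6.1. The Aim 2 test in 5.6.2b uses p=0.005, and the examples in 5.6.3 turn mainly on direction.

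Three further points stand in part:
- **Target.** If the estimand is activity actually done in the 28 days, the dilution is smaller, as the last column of the table shows. The plan does not say which is meant, but its language of cumulative effects makes underlying frequency a reasonable reading.
- **ActiGraph.** Continuous thigh wear in weeks 1-4 helps for walking, standing and sitting. The device is optional (5.1), and the activity types listed in 5.5 do not include bending, lifting, twisting, kneeling, climbing or crawling.
- **Power simulation.** It reuses the Aim 1 simulated data, so it may already contain the sampling error. That would protect the power claim, not the reported slope.

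On the early-late contrast, only the weeks 5-8 alternative is affected, and it is a sensitivity analysis.

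**Conclusion.** The point holds as a bias of unstated size. Followed as written, the plan reports self-reported Aim 2 slopes that are biased toward zero. With underlying frequency as the target and all 12 reports, the dilution is about 7-26% at ICCs of about 0.20 to 0.52. Those ICCs assume a simple two-sided slope model, power of exactly 80%, and the 65% taken on the proportion scale. Missed reports or a lower ICC make it larger; with 8 reports at ICC 0.20 it is 33%. With the 28-day percentage as the target and ICC 0.20 it is 14%. Walking, standing and sitting in ActiGraph wearers are less affected.

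The weeks 5-8 slope would be about 6-17% smaller than the weeks 1-2 slope with no true difference, in the direction the plan expects. The documents do not support extending this to weeks 3-4.

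The calculation covers sampling error only. Recall error and non-random missed reports could add to or change the bias and cannot be sized from the documents.

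**What to change.** For the self-reported categories:
- Report each activity's between-person ICC and the distribution of completed reports in weeks 1-4.
- In the long-term effects table, add a regression-calibrated slope with its interval beside the naive one. The exposure model would be a random-intercept logistic or beta-binomial model that includes the Aim 2 covariates.
- Keep the p=0.005 test on the naive slope.
- In the weeks 1-2 versus 5-8 contrast, calibrate both slopes or use equal numbers of reports per period.

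This needs no new data. The cost is a wider interval for the calibrated slope and a little more analysis. In a simulation with an assumed between-person SD of 15 points and a true slope of 3.85, the naive slope averaged 2.53 and a simple moment correction 3.84. Those data were generated to suit that correction, and the fuller model with covariates was not tried, so it should be tested on simulated data before use.

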## 5.7 Withdrawal of Subjects

### Participant withdrawals

We will record termination/withdrawal information for participants who decide to leave the study. Participants may leave the study at their own discretion, by contacting the research team and notifying them of the decision to leave the study. Participants may be withdrawn from the study without their consent if they become incarcerated during the study, or if the researchers feel that the study is in some way negatively affecting the participant's health or wellbeing. Participants may be withdrawn from the study without their consent if their responses to surveys are consistent with systematic non-compliance such as consistent non-completion or non-response to surveys not explained by other factors; findings indicating false data such as e-Questionnaire completion times that are too fast to be possible; or inappropriate and repeated completion of *ad hoc* flare window surveys even after explanation/clarification. Participants may also not be offered participation, or be withdrawn from the study, if they demonstrate threatening behaviors or potentially harmful behaviors towards research study staff.

Although not considered 'withdrawal' per se, participants who are consented may be subsequently excluded, if they fail the 2-week run-in period requirements as described above. For the purposes of the Information Statement, to simplify understanding for potential participants, we do not distinguish between withdrawals and these pre-randomization exclusions.

## 6.0 Reporting

There are no study-related processes in this purely observational study that would be expected to cause serious adverse events. [E-Questionnaires inquire about musculoskeletal pain conditions and treatments, other diagnoses, sociodemographic factors, and factors related to healthy living and lifestyle](#). We do not anticipate these to pose any significant effect on a participant's health or well-being, although it is theoretically possible (although highly improbable) that some questions may cause emotional distress or discomfort due to participants paying more attention to areas where musculoskeletal pain may or may not be present. Any possible discomfort or distress is expected to be negligible, and of note e-Questionnaires do not include question items pertinent to sensitive issues such as suicide risk, stigmatized behaviors, sexual trauma, etc. We will take the steps outlined in the IRQ to mitigate any possible discomfort or distress for participants when answering questions in the e-Questionnaires.

We will collect safety information regarding problems that are reported in an *ad hoc* basis to study staff by participants who complete informed consent for the VA component of this study as described in this human subjects application. Safety information will be collected via any applicable means (verbal and/or written communication) at the time of occurrence, but we will suggest that participants contact research staff by telephone. Safety information, including unexpected serious adverse events or problems, will be reported in accordance with VHA Handbook 1058.01. Collection of safety information will begin at study initiation. Collection of safety information will end at study closeout. Study staff will report safety information to the PI [name] at the time of occurrence. Events will be communicated via any applicable means (verbal and/or written communication). An adverse event or problem will be communicated to the IRB in writing using forms such as the 1) Unanticipated Serious Adverse Event or Problem Report, or 2) Continuing Review Questionnaire or Research Project Termination Report. An adverse event or problem will be communicated to the IRB in writing 1) within 5 business days of becoming aware of any serious unanticipated problem involving risks to subjects or others in VA research, or 2) at the time of study renewal or closure, whichever comes first, if the event is not serious or unexpected. Unauthorized research-related access, use, disclosure, transmission, removal, theft, or loss of VA sensitive information, including but not limited to PHI, individually-identifiable private information, confidential information, and Privacy Act-protected information will be reported within 1 hour of becoming aware of the event. Data for reporting will be compiled at the time of study renewal or closure.

## 7.0 Privacy and Confidentiality

The study will use participants' Protected Health Information (PHI) for the purposes of participant payment by mailed checks to the participant's current address. Also, PHI will be used to contact participants via telephone (as outlined above). PHI will be contained in the crosswalk file that links participant identifiers with the study-specific StudyID. No PHI will be disclosed at any point in the study.

We will take multiple steps to protect participants' privacy, confidentiality, and inappropriate disclosure of data, under strict VA security guidelines. All study staff will maintain current on required

VA trainings for privacy and confidentiality. Data will be stored in Participant Data Files that will be de-identified, labeled with a code number that is unique to each patient in the study ('study-specific StudyID'). The study-specific StudyID will be a unique numerical code consecutively numbered in order of approach/screening. We will NOT include any protected health information (PHI) in the Participant Data Files. The Participant Data Files will be stored in a secure password-protected electronic location on the VA servers (expected to be the in the J: drive on the Health Services Research & Development (HSR&D) server), accessible only to study staff members and authorized personnel. Staff will maintain a Master List key code that links participants with the study-specific StudyID. This Master List key code will be stored in a secure password-protected electronic location on the VA servers, separately from all other study data. All hard copy files such as signed informed consent forms (from prior to the time when these were replaced by Information Statements) .will be stored in locked filing cabinets in the locked/secured offices of the Seattle ERIC, while all electronic data will be stored in password-protected files in a limited access folder (to research staff) on a secure VA network drive. Only IRB-approved study personnel will have access to Participant Data Files or Informed Consent Forms. We will only analyze data that does NOT contain PHI, and will report participant data in aggregate form only- no PHI will be entered into analyses or reports.

If improper use or disclosure of research data occurs, the ISSO and Privacy Officer will be notified within one hour of the improper use or disclosure, and we will also adhere to any other local policies regarding improper use or disclosure.

Of note, no wireless or remote data sharing will be enabled on the ActiGraph, so no data can be transmitted in this way, safeguarding data and participants' privacy.

## 8.0 Communication Plan

This study involves VAPSHCS as the coordinating center and UW as a participating site. When the initial application to conduct human subjects research (related to the non-VA component of this study) was submitted to the UW IRB by UW researchers, we provided a letter notifying the UW IRB of the existing VAPSHCS IRB approval and a copy of the VAPSHCS IRB approval letter. For any future modifications to the UW IRB-approved research processes, we will coordinate with UW researchers who will submit documentation to the UW IRB if appropriate; due to the study's minimal risk, the UW IRB has indicated that they only want to receive updated documentation if major, substantiative changes are made to the study processes. If such changes occur, we will provide the appropriate documents to the UW IRB.. If we are told a particular document cannot be shared with the UW IRB and UW researchers, we will share a summary of the document's contents instead.

At the time of any PRAF or modification submitted to the VAPSHCS IRB, we will submit relevant human subjects approvals from UW and documents approved by the UW IRB that have changed since the last PRAF or modification. Conversely, at the time of any modification submitted to the UW IRB, we will share the most recent VAPSHCS IRB approval letter unless previously shared, and either pertinent VAPSHCS IRB-approved documents, or summaries of such documents, according to the guidance provided by the VAPSHCS IRB or IRB administrators. In instances where we are told that VAPSHCS

IRB-approved documents or summaries are not required with UW IRB modifications, we will not submit such documents.

There are no expected AEs or serious AEs involved with this purely observational research. We will work with UW researchers to ensure that UW researchers report SAEs or unanticipated problems (UAPs) to our VAPSHCS research team within 5 days of becoming aware of the SAEs or UAPs. The study design does not permit the sharing of individual-level VA data outside of the VA during the study. Therefore, if SAEs or UAPs are reported to or otherwise learned of by VA research staff, we will advise participants to contact UW research staff and report this information. Where applicable, information on SAEs or UAPs can also be shared with UW researchers in aggregate form.

